Early Activation of Artificial Urinary Sphincter: A Pilot study

Abstract:

Urinary incontinence or loss of bladder control is a troublesome issue for all affected patients. The causes of urinary incontinence and its treatment options vary widely. A commonly encountered reason for urinary incontinence in men is related to treatment for prostate cancer. These treatment options can range from surgical removal of the prostate, external beam radiation therapy, and/or brachytherapy, the insertion of radioactive implants directly into the tissue. Mild cases of incontinence are responsive to more conservative measures, but moderate to severe cases often require placement of an artificial urinary sphincter. Typically, these devices are left deactivated for a period of 4- 6 weeks following implantation to allow swelling to subside before use. We hypothesize that the device could be activated within an earlier timeframe without increasing the risk of complications. No studies to date have evaluated this; therefore we plan to conduct a prospective study in which we will activate the device 3 weeks after placement and monitor for complications.

Aim of the study:

To assess the safety and feasibility of early activation of an artificial urinary sphincter and assess whether or not this increases the risk of postoperative complications. We hypothesize that a period of 3 weeks should allow adequate time for the resolution of urethral and scrotal swelling following artificial urinary sphincter placement, and that activation of the device at that time, as opposed to traditional 4-6 weeks post-operatively, will lead to improved patient satisfaction with no increase in postoperative complications.

Background:

Urinary incontinence is one of the most common complications following surgical treatment of prostate cancer via radical prostatectomy. All patients will have this to some degree in the initial post-operative period, but it typically resolves over time as the newly created urethrovesical anastomosis heals. Wolin et. al reported a 59% rate of urinary incontinence at 6 weeks post-prostatectomy among studied patients¹. For the unfortunate patients who have persistent incontinence requiring the use of multiple pads per day in the absence of a bladder neck contracture or stricture, an artificial urinary sphincter (AUS) may be the best option to regain continence.

The AUS was first introduced into practice in 1972 at the Baylor College of Medicine. Since that time, it has been found to effectively improve the quality of life of patients with post-prostatectomy urinary incontinence. In a recent analysis, 79% of patients report being satisfied and using no more than one pad per day². The device has undergone numerous revisions since its introduction and the current model, the American Medical Systems (AMS) 800, is widely implanted throughout the U.S. and worldwide. Several studies have been performed validating the AUS as a surgical treatment of post prostatectomy incontinence. There have been varying degrees of success documented in the literature secondary to the different definitions of success used, however, using the definition of zero to 1 pad per day, success rates have varied between 60% and 90% in modern series(3). The most common

complication is urinary retention, which can be managed with a urethral catheter. Less common complications include infection, device malfunction, and urethral erosion³.

The device (see figure 1) is placed in the operating room under general anesthesia. The device consists of a urethral cuff, pressure regulating balloon, and an activation pump and once activated, the urethral cuff will be closed at rest. The patient will squeeze the scrotal pump to open the cuff in order to void once the need arises. Patients are typically discharged the same day without a Foley catheter, unless unable to void in the recovery room. The device is typically left in the de-activated position to allow reductions in urethral edema and scrotal edema before the patient is allowed to manipulate the device. The device is routinely activated at 4-6 weeks post-operatively⁴. A literature review did not reveal any papers or guidelines that show that this period of de-activation of 4-6 weeks is actually required, though Baylor College of Medicine reports current practice of only waiting 4 weeks until activation⁵. There have not been any studies conducted indicating any negative consequences of activating the device early and there have been two or three patients at CAMC who have activated their device a few days post discharge from the hospital, against our advice.. These patients did not report any adverse events with early activation.

There are possible complications associated with AUS placement. Complications that occur less often include bleeding, infection, urinary tract injury, device erosion, wasting away of muscle mass in the urinary tract known as sub cuff atrophy, or loss of bladder control. Complications that may occur occasionally include persistent loss of bladder control or Mechanical Failure of device. These are risks associated with any AUS procedure and patients participating in this study will not be at higher risk for these than those who chose not to participate.

[figure not shown]

Figure 1. Implanted Artificial Urinary Sphincter (AUS) demonstrating attachments of the cuff to the pressure regulating balloon and intra-scrotal pump4.

Reconstructive Urology, Urology and Urodynamics

[figure not shown]
[figure not shown]

Figure 2 Artificial Urinary Sphincter (AUS)

An artificial urinary sphincter is used to treat stress incontinence in men, which is caused by urethral dysfunction (usually after prostate surgery). Additionally, this procedure is performed in both men and women with sphincter dysfunctions related to spinal-cord injury or multiple sclerosis. Before resorting to this treatment, most experts advise using medication and bladder-retraining therapy. Alternatives to this procedure include the pubovaginal sling in women, or the periurethral injection of collagen in both men and women.

adam.com

Figure 3 Implanted AUS

An artificial sphincter consists of: a cuff that fits around the bladder neck a pressure regulating balloon a pump that inflates the cuff to treat urinary incontinence, a cuff is placed around the bladder neck so that when it is inflated, the urethra closes tightly. The pressure-regulating balloon is placed under the tissues of the lower abdomen. The balloon is then filled with liquid (occasionally, an iodine-based solution is used so that it will be visualized when x-ray procedures are performed). The control-pump mechanism is placed in the labia for women, and in the scrotum for men. To use the sphincter, compress (squeeze) the pump so that fluid is diverted from the urethral cuff to the balloon. This action enables the sphincter to relax, which in turn, enables you to urinate. The cuff re-inflates on its own in three to five minutes.

[figure not shown]

Figure 4 Inflation of AUS

When inflated, the cuff constricts the urethra and blocks the passage of any urine. When deflated, the cuff reduces pressure on the urethra and allows for the free passage of urine.

[figure not shown]

Figure 5 AUS with Foley catheter

A foley catheter is also inserted during surgery, which is removed prior to discharge from the hospital. The artificial sphincter cuff is not inflated immediately after surgery, in order to allow the tissues to heal.

Significance:

Post-prostatectomy urinary incontinence is a troubling complication following treatment (radical prostatectomy, radiation therapy, or brachytherapy) for prostate cancer, or in rare instances the treatment of benign prostatic hypertrophy, and significantly decreases quality of life in affected patients. An artificial urinary sphincter has been found to significantly improve quality of life in these patients. Providing data which demonstrates the safety and feasibility to activate an artificial urinary sphincter 3 weeks after surgery as opposed to 4-6 weeks will allow men to regain their continence earlier, therefore improve their quality of life.

Methods

Study Design:

The design will be a single institute prospective study with patients undergoing artificial urinary sphincter placement by the operating surgeon, [name] at Charleston Area Medical Center in Charleston, WV. All patients following informed consent that meet the inclusion criteria are eligible to participate in the study.

Sample:

All male patients with moderate to severe urinary incontinence who have been treated for prostate cancer (radical prostatectomy, External Beam Radiation therapy or brachytherapy, or Incontinence related to trans urethral resection of the prostate (TURP) or simple prostatectomy undergoing artificial urinary sphincter placement at Charleston Area Medical Center by [name], D.O. will be offered the chance to participate in this study. This is a pilot study and thus no power analysis to calculate necessary sample size is conducted to determine a number that would yield sufficient power. We will aim to enroll 25 patients, which we anticipate to be accrued within 3 years from the start of the study. We will have 1 study group: those who are activated at 3 weeks post implantation.

Inclusion Criteria:

All patients undergoing artificial urinary sphincter (AUS) placement by a single surgeon, [name].

Exclusion Criteria:

Any patient who has previously undergone artificial urinary sphincter placement and presents for revision or additional cuff placement.

Any patient who is undergoing combined artificial urinary sphincter and inflatable penile prosthesis placement.

Any patient who is a poor candidate for early activation due to poor condition at presentation or signs of infection.

Procedures and Protocol:

There isn't a comparison group for this study; therefore all patients agreeing to participate will have the urinary sphincter activated 3 weeks after surgery. If there are patients that later choose not to have early activation or are found to be poor candidates for three week activation based upon their post op

exam, we will proceed with activation at a 4-6 week time period. While there is no comparison group in the study, patient satisfaction and adverse events for study patients will be compared to historical literature.

Currently patients are not routinely seen for a 3 week follow up appointment, so approximately \$3000 will be requested from Research appropriations to cover the costs of this study. All other costs are standard of care, so patient will be responsible for those costs whether they agree to enroll in the study or not. The money from the CAMC Research Appropriations will be used to cover all the clinical fees for the 3 week visit to activate the AUS.

Pre-procedure:

- 1. All eligible patients will be informed about the study at their regularly scheduled pre-operative office visit. If the patient agrees to participate, they will be consented with the consent form as written. A note is made in the progress note of the patient's chart detailing the consent.
- Original signed consent will be kept and stored in the consent binder at [name] office and one copy of the consent will be placed in the medical record and another will be given to the participant.
- 3. Patient will complete an SF-8 quality of life survey and Incontinence Impact Questionnaire (Appendix A).

Intraoperative procedures:

1. Once consented, the patient will undergo the procedure without any changes to our normal routine. The patient's device will be deactivated at the conclusion of the procedure.

Post-procedure:

- 1. The patient will be discharged post-operatively (same day) and follow-up will be arranged in 3 weeks to activate the device.
- 2. Study patients have a follow up office visit at 3 weeks (up to 3 weeks and 3 days after the procedure) which includes a post-operative evaluation of their incisions, degree of bruising, tissue induration, tenderness and accessibility of the pump. If these factors are acceptable and pump mechanics are normal, the artificial sphincter will be activated and the patient will be educated on its proper use.
- 3. Additional follow up will include the regular 6 week visit, a visit at 3 months, and then every 6 months for a total of 1 year unless issues arise that necessitates deviation. At each visit, patients will complete the Incontinence Impact Questionnaire and the SF-8 quality of life survey.

Study Chart:

INFORMATION	PRE-	Intra-	POST-Treatment	POST-	POST-	POST-	POST-Operative
	Treat	operative	3 weeks	OperativeTrea	Operative	Operative	Treatment 1 year
	ment	Treatment	(up to 3 weeks and	tment	Treatment 3	Treatment	(+ 1 month)
			3 days after	6 weeks	months	Six months	
			procedure)	(+ 1 week)	(+ 2 weeks)	(+ 3 weeks)	
Inform Subject	Х						
Consent Subject	Х						
Note in Record	Х						
Office visit	Х		Х	X	Х	Х	Х
SF-8 survey administered	Х			Х	Х	Х	Х
Incontinence Impact Questionnaire	Х		Х	Х	х	Х	Х
Procedure conducted		Х					
Data Collection	Х	X	Х	Х	Х	Х	Х

Data Collection and Management:

The SF-8 is a quality of life instrument related to health functioning that provides an eight question brief assessment of physical and mental health⁶. It has been found to have adequate reliability and validity in prior studies for quality of patient life and it incorporates a manual for easy interpretation.⁷. The Incontinence Impact Questionnaire short form was adapted from a survey that was developed for women with stress incontinence. This questionnaire has been validated for use in men after radical prostatectomies and consists of 7 items in which measures the effect of Urinary Incontinence on quality of life⁸.

Following surgery, patient characteristics and operative details will be recorded. These will include:

- Medical Record Number
- Patient name
- Age
- BMI
- Operative time
- Artificial sphincter cuff size
- Pressure-regulating balloon size
- Intra-operative complications (urethral injury, bleeding)
- Reason for AUS placement (Post-prostatectomy, Radiation therapy for prostate cancer, or Incontinence related to TURP)
- Finish date of prostate cancer treatment or TURP
- Preoperative daily pad usage
- Pre-surgery SF-8 survey
- History of medication
- Date device is activated
- Comorbidities
- ECOG Score

- ASA Score
- Tobacco Use
- Diabetes

When the study patient follows up at 3 weeks postoperatively, we will assess for immediate postoperative complications:

- Post-operative urinary retention Y/N
- Bleeding Y/N
- Presence/concern for infection Y/N
- Presence/concern for urethral erosion Y/N

When any patient follows up at 6 weeks, 6 months, and 12 months postoperatively, we will assess:

- Postoperative daily pad usage
- Perceived improvement in incontinence (scale 1 (none) 10 (very satisfied))
- Presence/concern for infection Y/N
- Presence/concern for urethral erosion Y/N
- Post-surgery SF-8 surveys (6 weeks, 3 months, 6 months)

Statistical Analysis:

The Center of Health Service and Outcomes Research will conduct the data analysis. For this exploratory study, selection of appropriate statistical measure will be determined by CAMC Center for Health Education and Research Institute. Specific tests will be determined by whether the data is continuous or categorical. Descriptive statistics will be used as appropriate and comparisons will be done using student's T-test and chi-square test. In addition univariate and multivariate multiple logistic regressions will be used to determine which variables predict patient's outcomes. All comparisons will be done at 95% of level of significance.

I. Human Subjects

Study population: All patients undergoing artificial urinary sphincter (AUS) placement by a single surgeon, [name] at Charleston Area Medical Center.

Recruitment methods: All patients, following informed consent, that meet the inclusion criteria are eligible to participate in the study. Patients will be consented by the principal investigator only at time of usual surgical informed consent using the attached consent form. Consent will be obtained prior to the surgical procedure.

Benefits: Early activation of the artificial urinary sphincter will allow the patient to regain continence earlier.

Risks and discomforts: The principle risks of participation in this study will be the standard risks of the operation.

Less often, there are risks of bleeding, infection, urinary tract injury, device erosion, wasting away of muscle mass in the urinary tract, or loss of bladder control.

Occasionally, there are risks of persistent loss of bladder control or mechanical failure of device.

Sexual Activity: All patients will be asked to refrain from sexual activity for 4-6 weeks following surgery, which is our current standard post-operative course.

Consent Process: [name] will consent eligible patients at their office visit prior to scheduling the procedure. Patients will be educated on the study and told that if they do not wish to participate, they will receive the usual care which is activation of device at the 6 week checkup.

Confidentiality: Taking part in this research study requires doctor and assistants to review all medical records as may be needed for purposes of this study. Any release of information derived from these medical records to scientific organizations, medical journals, etc. will be done only without identification of the study participants. All study records will be held in strict confidence. Patient's records may be inspected by governmental agencies such as the DHHS, including FDA, and CAMC/WVU Institutional Review Board. They may inspect patient's records for the purposes of this study and/or audit while maintaining your records as confidential to the extent required by the law. The results of this research study may be presented at meetings or in publications. Patient's identity will not be disclosed in those presentations.

Costs to subjects: There will be no additional costs associated with patient's participation in this study. Costs for additional visit at 3 weeks to activate the AUS will be covered from grant funding requested from the CAMC Research and Grants Office's Research appropriations. Patient will accrue no costs for participation in this study. Routine costs will be billed in the customary manner. We do not anticipate any additional cost to the patient.

Payments to subjects: There will be no payments to subjects for participating in this study.

Debriefing: If the patient chooses not to participate in the study then he will receive the current management which includes office follow-up at 4-6 weeks postoperatively for activation of the device.

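### The one study group is defined by activation at 3 weeks, a result known only after enrolment, and no analysis set says whether deferred men count in the comparison with the literature

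*Combined protocol and SAP*

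**What the plan says.** The aim is stated as "To assess the safety and feasibility of early activation of an artificial urinary sphincter". Under Sample, the plan sets the target, "We will aim to enroll 25 patients", and then gives its only explicit definition of the group: "We will have 1 study group: those who are activated at 3 weeks post implantation".

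Procedures and Protocol begins from the intention that everyone follows one schedule: "There isn't a comparison group for this study; therefore all patients agreeing to participate will have the urinary sphincter activated 3 weeks after surgery". The next sentence provides for exceptions. Men who change their minds, or who are "found to be poor candidates for three week activation based upon their post op" examination, are handled differently: "we will proceed with activation at a 4-6 week time period". Post-procedure makes activation at the 3-week visit conditional on the state of the incisions, bruising, induration, tenderness, access to the pump and pump mechanics. Recruitment methods places consent before surgery.

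The external benchmark is described in these words: "patient satisfaction and adverse events for study patients will be compared to historical literature". The term used there, *study patients*, is not defined. Statistical Analysis names types of test but no analysis set, and it does not say how deferred men are counted.

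**The concern.** A group defined by what happened at the 3-week visit is selected on early recovery. Retention, bleeding, infection and erosion are assessed at the same visit that decides activation. A man with a worrying finding there could be deferred, fall outside the group as Sample words it, and take his event with him. The literature series that serve as the benchmark are not described as selected in this way.

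Men who decline early activation by choice would leave the group too. They may have fewer events than the rest, so the effect can run in either direction.

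Feasibility is the other half of the aim, and the plan states no measure for it. Within a group made up only of men activated at 3 weeks, a proportion activated carries no information.

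**Working it through.** The plan states no figure to reproduce. The enrolment target of 25 comes with no power analysis, and no deferral share or event rate is given. The check therefore has two parts: the wording, and an illustration with assumed counts.

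**Wording, side by side**

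| Section | Term | Natural reach |
|---|---|---|
| Sample | study group | men actually activated at 3 weeks |
| Procedures and Protocol, literature comparison | study patients | not defined; follows directly after the deferral sentence |
| Post-procedure | study patients: "Study patients have a follow up office visit at 3 weeks" | men not yet activated, so all implanted participants |
| Data Collection and Management, later visits | any patient | no restriction by activation date |
| Intervention | study group | participants as opposed to non-participants |
| Statistical Analysis | none | no set named |

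Two readings are open, and they differ exactly by the deferred men.

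**Effect on the complication rate**

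Let n be the men implanted, d the men deferred, e the deferred men with an event and k the activated men with an event.

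- Literal Sample group: k/(n − d)
- All implanted men: (k + e)/n
- For d > 0, the literal rate is the lower one exactly when e/d > k/(n − d), that is, when deferred men have the higher event rate.

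Intervals are two-sided exact (Clopper-Pearson) 95%. For x events in m men, the lower limit is the 2.5% quantile of Beta(x, m − x + 1) and the upper limit is the 97.5% quantile of Beta(x + 1, m − x). The lower limit is 0 when x = 0, and the upper limit is 100% when x = m. All counts below are assumed.

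| n | d | e | k | Literal group | All implanted | Shift (points) |
|---|---|---|---|---|---|---|
| 25 | 0 | 0 | k | k/25 | k/25 | 0 |
| 25 | 3 | 3 | 0 | 0/22 = 0% (0 to 15.4) | 3/25 = 12.0% (2.5 to 31.2) | −12.0 |
| 25 | 3 | 2 | 1 | 1/22 = 4.5% (0.1 to 22.8) | 3/25 = 12.0% (2.5 to 31.2) | −7.5 |
| 25 | 5 | 0 | 2 | 2/20 = 10.0% (1.2 to 31.7) | 2/25 = 8.0% (1.0 to 26.0) | +2.0 |

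Consent precedes surgery, so fewer than 25 men may be implanted. With 23 implanted, the second row becomes 0/20 = 0% (0 to 16.8) against 3/23 = 13.0% (2.8 to 33.6). The last row becomes 2/18 = 11.1% (1.4 to 34.7) against 2/23 = 8.7% (1.1 to 28.0).

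These rows are examples, not bounds. With 5 of 25 deferred and five events, all in deferred men, the rates are 0/20 = 0% against 5/25 = 20%, a shift of −20 points. With all five events in activated men they are 5/20 = 25% against 5/25 = 20%, a shift of +5 points. One set is nested in the other, so overlap of the paired intervals says nothing about whether the choice of set matters.

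**Effect on feasibility**

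In the literal group the proportion activated is (n − d)/(n − d) = 100% for any d. Over 25 implanted men it is:

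- no deferrals: 25/25 = 100% (86.3 to 100)
- one deferral: 24/25 = 96.0% (79.6 to 99.9)
- three deferrals: 22/25 = 88.0% (68.8 to 97.5)
- five deferrals: 20/25 = 80.0% (59.3 to 93.2)

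**The case against.** The Sample sentence may do no more than announce a single-arm design. It sits next to the enrolment target, and Procedures and Protocol says that all participants are to be activated at 3 weeks. The literature comparison speaks of study patients, not of the study group, and Post-procedure uses that term for men whose activation is still undecided. This stands. A reader might infer that the plan excludes deferred men, or that the literal definition is the only one an analyst could use. The documents support neither inference: no passage removes these men, and the all-enrolled reading is at least as available.

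A second objection is that the question concerns early activation, and men activated at 4-6 weeks received the usual timing. Counting them dilutes the exposure and could hide an increase after early activation. This also stands. It is a reason to show both sets, not to rely on either alone.

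Third, this is an exploratory, unpowered pilot, and the activation date is recorded, so both sets can be rebuilt afterwards. That limits the harm. It does not remove it, because the choice between two open readings could then be made with the results in view.

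Finally, no passage says that feasibility would be computed within the Sample group. The missing feasibility measure is a gap in its own right, and the 100% result follows only if that group is used.

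**Conclusion.** The concern holds as a matter of inconsistent wording and an undefined analysis set. The only explicit definition of the group depends on a result after enrolment, and the plan itself foresees enrolled men who would not meet it. Followed literally, the definition would drop those men from the adverse-event and satisfaction comparison with the literature and make any activation proportion uninformative.

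The size cannot be determined from the documents. It is zero if nobody is deferred. Otherwise its direction depends on whether deferred men have more or fewer events than activated men. A reader might take the tabulated shifts as the likely range; they rest wholly on assumed counts and show only that, with about 25 men, reassigning a few can change the headline from no complications to some.

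The point should be fixed before analysis, chiefly because the correction is cheap. Confidence is medium, since the authors may have intended all enrolled men throughout.

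**What to change.** - Replace the Sample sentence with: *The study group is all consented men who receive the AUS, with activation planned at 3 weeks, whatever the actual activation date.* Use that term consistently in Procedures and Protocol, Post-procedure, Data Collection and Management, and Intervention, and name the set in Statistical Analysis.
- Report feasibility as the proportion of that set activated by 3 weeks and 3 days, the visit limit already in the protocol. Give an exact 95% interval and the reason for each deferral (examination finding or patient choice).
- Report complications and satisfaction side by side in all implanted men and in men activated at 3 weeks, and set both against the literature. Include the listed intra-operative complications. Separate findings at the 3-week visit, which precede activation, from infection and erosion at later visits.
- State whether the third exclusion criterion, on poor candidates for early activation and signs of infection, applies only before surgery. It needs to be reconciled with the deferral rule. No change is proposed to when any device is activated.

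The cost is protocol wording plus one new data item, the reason for deferral. Activation date and the complication items are already collected. The downside is that rates may look less favourable and that the all-implanted set includes some men activated at 4-6 weeks; the parallel table for men activated at 3 weeks addresses the latter.

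### No rule requires capture of complications treated between fixed visits, or continued assessment of men whose follow-up deviates, so some of these data may be missed

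*Combined protocol and SAP*

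**What the plan says.** The aim includes to "assess whether or not this increases the risk of postoperative complications" (Aim of the study). There is one group of 25 men (Sample), and "patient satisfaction and adverse events for study patients will be compared to historical literature" (Procedures and Protocol).

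Post-procedure item 3 sets visits at 6 weeks, 3 months and then "every 6 months for a total of 1 year unless issues arise that necessitates deviation". It does not define the issues, say whether visits are added, moved or omitted, or say what is recorded afterwards. It adds: "At each visit, patients will complete the Incontinence Impact Questionnaire and the SF-8 quality of life survey".

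Data Collection and Management attaches the clinical items to named visits:

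- "When the study patient follows up at 3 weeks postoperatively, we will assess for immediate postoperative complications": retention, bleeding, infection and erosion, each yes/no.
- "When any patient follows up at 6 weeks, 6 months, and 12 months postoperatively, we will assess": pad use, perceived improvement, infection and erosion.

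A typical item reads "Presence/concern for urethral erosion Y/N". There is no onset date and no look-back period.

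The Study Chart marks a general data-collection row at every scheduled visit, including 3 months, but does not say which items it covers. It has no column for unscheduled visits. The Confidentiality paragraph says that taking part "requires doctor and assistants to review all medical records as may be needed for purposes of this study".

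**The concern.** The deviation clause is triggered by problems, and problems are what this study sets out to count. If a complication is treated between visits and has resolved by the next one, a yes/no item with no look-back can truthfully be answered no. If a visit is moved or omitted because of the complication, no rule secures that man's later pad use or questionnaires.

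Retention shows the gap most clearly. The Background calls it the most common complication and says a catheter can manage it, so it may be brief. Its only listed field is at 3 weeks, the visit at which the device is switched on. Retention that follows activation has no listed field at any later visit.

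The loss would not be random. Missed events lower the observed complication rate, and missing outcomes from affected men leave later results weighted towards uneventful courses. With no concurrent control arm treated the same way, under-capture has nothing within the study to offset it.

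**Working it through.** The plan states that no power analysis was done, so it has no figure of its own to reproduce. The check sets the schedule against the listed items and then gauges scale.

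**1. What is listed where**

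| Item | 3 wk | 6 wk | 3 mo | 6 mo | 12 mo | Unscheduled |
|---|---|---|---|---|---|---|
| Retention, postoperative bleeding | yes | – | – | – | – | – |
| Infection, erosion | yes | yes | – | yes | yes | – |
| Pad use, perceived improvement | – | yes | – | yes | yes | – |
| General data-collection row (Study Chart) | yes | yes | yes | yes | yes | – |

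**2. Spacing of the listed infection and erosion checks**

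- 6 weeks to 6 months: 26 − 6 = about 20 weeks.
- 6 to 12 months: 52 − 26 = about 26 weeks.
- If the 3-month visit did collect these items, the first gap would split into 13 − 6 = 7 weeks and 26 − 13 = 13 weeks.

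**3. Weight of one event**

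1/25 = 4 percentage points. Exact (Clopper-Pearson) 95% intervals:

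- 0/25 = 0% (0 to 13.7%)
- 1/25 = 4% (0.1 to 20.4%)
- 2/25 = 8% (1.0 to 26.0%)

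**4. Chance of missing at least one event**

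Let p be the true 1-year risk per man and m the share of events that go unrecorded. The documents give neither, so both are assumptions. With independent men and at most one event each:

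P(at least one missed) = 1 − (1 − p·m)^25

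| p | m = 25% | m = 50% | m = 75% |
|---|---|---|---|
| 4% | 22% | 40% | 53% |
| 8% | 40% | 64% | 79% |
| 12% | 53% | 79% | 91% |
| 20% | 72% | 93% | 98% |

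For example, with p = 8% and m = 50%: 1 − (1 − 0.04)^25 = 1 − 0.36 = 64%.

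For the same pair, the chance that no event at all is recorded is (1 − 0.08 × 0.5)^25 = 36%. With full capture it is (1 − 0.08)^25 = 12%.

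**The case against.** A reader might infer that men with problems leave follow-up and that their events and outcomes are lost. The documents do not say so. Deviation may simply mean extra or moved visits, and no section says that these men stop, skip forms or have data discarded. Silence on capture is not exclusion of it.

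There are also real routes by which events could be found:

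- Record review is provided for, and with one surgeon at one institution many treated events should be in accessible notes.
- The Study Chart calls for data collection at 3 months.
- The questionnaire sentence could be read to include unscheduled visits.
- The planned comparison refers to adverse events generally, which is broader than the listed items.
- A complication still present at the next fixed visit would be recorded, and the yes/no items do not expressly limit themselves to the day of the visit.

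These points rule out a claim of certain loss. They do not close the gap. Record review appears only under Confidentiality, as a permission not tied to finding complications. The 3-month row names no complication items. The each-visit sentence covers the two questionnaires, not complications or pad use.

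Two further inferences should be resisted. Most of the year falls between visits, but that is so in any visit-based study and does not measure loss. Nor is it certain that the comparison with the literature would favour early activation, since that also depends on how the published series counted events, which the documents do not show.

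**Conclusion.** The concern holds as a risk, not as an established loss. Followed as written, the schedule can miss complications that arise and resolve between listed visits, including retention after activation, and it does not secure the later outcomes of men whose follow-up deviates. Any such loss would tend to understate complications and flatter later pad-use and quality-of-life results in this cohort.

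The size cannot be fixed from the documents. The range of about 22% to 98% for at least one missed event rests wholly on the assumed risks (4% to 20%) and missed shares (25% to 75%). If record review is in fact done systematically, the missed share could be below that range. What needs no assumption about rates is that one event is worth 4 percentage points in 25 men. In a single-arm safety study that is reason enough to amend the data-capture rules.

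**What to change.** Amend data capture only:

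1. In Post-procedure item 3, state that a deviation may add or move visits, but that every enrolled man keeps the scheduled study assessments to 1 year unless he withdraws consent for data collection. If he cannot attend, take questionnaires and pad use remotely, provided the consent allows it. The consent form was not available for this review, so that must be checked.
2. In Data Collection and Management, record retention, bleeding, infection and erosion, with onset dates, at every scheduled visit including 3 months and at any unscheduled visit. Word each item to cover the period since the last visit.
3. Add an unscheduled-visit column to the Study Chart, and require the complication items to be checked against the medical record.
4. In Statistical Analysis, report cumulative 1-year complications in all implanted study patients.

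The cost is a wording amendment, one short form, some chart review and occasional phone contacts. No procedure is added and clinical management is untouched.
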